### **8.3. Data Handling Conventions**

By-subject listings will be created for important variables from each eCRF module. Summary tables for continuous variables will contain the following statistics: N (number in population), n (number with data), mean, standard deviation (StD), 90% confidence intervals (CIs) on the mean, median, minimum, and maximum. Summary tables for categorical variables will include: N, n, percentage, and 90% CIs on the percentage. Unless otherwise indicated, 90% CIs for binary variables will be calculated using the binomial distribution (exact method) and will be 2-sided. Data will be described and summarized by relevant dose level, analysis set, and time point. As appropriate, changes from baseline to each subsequent time point will be described and summarized by dose level. Similarly, as appropriate, the best change from baseline during the study will also be described and summarized by dose level. Graphical techniques (eg, waterfall plots, Kaplan-Meier curves, line plots) may be used when such methods are appropriate and informative.

The baseline value will be the last (most recent) pre-treatment value. Data from all sites will be pooled for all analyses. Analyses will be based upon the observed data unless methods for handling missing data are specified. If there is a significant degree of non-normality, analyses may be performed on log-transformed data or nonparametric tests may be applied, as appropriate.

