3. C1D1 Vital Signs will be taken within 15 min pre-GS-5829 dose and 2 and 4 hours post dose (+/- 15 min); vital signs will be taken pre-dose only at all subsequent visits. Oxygen saturation will be tested with a pulse oximeter.
4. Triplicate ECG will be collected at any time during Screening window, Day 1 of Cycles 2-6 (at pre-dose), and at EOT. In Phase 1b monotherapy, triplicate ECGs will be collected on C1D1 at pre-dose and 1-4 hrs post-dose and on C1D8 at pre-dose, 1 hour, 2 hours, 3 hours, 4 hours, 6 hours, and 8 hours post dose (+/- 20 min). In Phase 2 dose expansion, triplicate ECGs will be collected on C1D1 at pre-dose and 1-4 hrs post-dose and on C1D8 at pre-dose, 1 hour, 2 hours, 4 hours, and 6 hours post dose (+/- 20 min). ECGs should preferably be collected prior to PK (or any other blood draw) if they are to be collected at the same nominal time point. Subjects should be resting quietly and free of distraction (eg, TV, conversation) for 10 minutes prior to ECG collection and ECGs should be collected over a 5 minute window at each time point.
5. Administer GS-5829 in a fed state on C2D1 in selected dose level.
6. Beginning on C1D1, subjects will receive GS-5829 daily.

7. Adverse event reporting period begins once the Informed Consent Form has been signed. AEs will be assessed using NCI CTCAE (v 4.03) criteria at pre- and post-GS-5829 dosing during applicable clinic visits. Subjects will also return to clinic at 30-day post last IP dose to assess AEs and SAEs. At screening, all medications taken up to 30 days prior to screening will be documented in the eCRF.
8. Screening chemistry, hematology, coagulation, and urinalysis to be collected within 7 days of C1D1 for central lab assessment.
9. Coagulation assessment includes PT/PTT, fibrinogen, Factor VII, fibrinogen degradation products (FDP).

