- Medical history includes significant past medical events (eg, prior hospitalizations or surgeries), a review of the disease under study, prior anti-cancer therapies, historical PSA levels and any concurrent medical illnesses.
- Screening and End of Treatment Physical Examinations (PE) will be a complete PE. Beginning at C1D1, a modified physical examination will be performed. Weight (without shoes) should be measured at each PE. Height (without shoes) is measured at Screening only.
- Study Day 1 vital signs will be take 15 min pre-enzalutamide dose. C1D1 Vital Signs will be taken within 15 min pre-GS-5829 dose and 2 and 4 hours post dose (+/- 15 min); vital signs will be taken pre-dose only at all subsequent visits. Oxygen saturation will be tested with a pulse oximeter.
- Triplet ECG will be collected at any time during Screening window, Day 1 of Cycles 2-6 (at pre-dose), and at EOT. In Phase 1b dose escalation with enzalutamide, triplicate ECGs will be collected on Cycle 1, Day 1 and Day 15 at pre-dose, 1 hour, 2 hours, 3 hours, 4 hours, 6 hours, and 8 hours post dose (+/- 20 min). In Phase 2 dose expansion, triplicate ECGs will be collected on C1D1 and C1D15 at pre-dose and 1-4 hrs post-dose and on C2D1 at pre-dose, 1 hour, 2 hours, 4 hours, and 6 hours post dose (+/- 20 min). ECGs should preferably be collected prior to PK (or any other blood draw) if they are to be collected at the same nominal time point. Subjects should be resting quietly and free of distraction (eg, TV, conversation) for 10 minutes prior to ECG collection and ECGs should be collected over a 5 minute window at each time point.
- AAG will be collected at Screening, pre-dose on C1D1 and C1D8 only
- Subjects in phase 1b dose escalation with enzalutamide and Phase 2 Group 2 or Group 3 receive enzalutamide alone beginning on Study Day 1, then in combination with GS-5829 beginning C1D1.
- Adverse event reporting period begins once the Informed Consent Form has been signed. AEs will be assessed using NCI CTCAE (v 4.03) criteria at pre- and post-GS-5829 dosing during applicable clinic visits. Subjects will also return to clinic at 30-day post last IP dose to assess AEs and SAEs. At screening, all medications taken up to 30 days prior to screening will be documented in the eCRF.
- Screening chemistry, hematology, and urinalysis to be collected within 7 days of C1D1 for central lab assessment.

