3.8.2. Analysis Visit Windows

The nominal visit as recorded on the CRF will be used when data are summarized by visit. Any data relating to unscheduled visits will not be assigned to a particular visit or time point.

However, the following exceptions will be made:

- An unscheduled visit prior to the first dosing of study drug may be included in the calculation of the baseline value, if applicable.
- Unscheduled visits after the first dosing of study drug will be included in determining the maximum postbaseline toxicity grade.
- For subjects who prematurely discontinue from the study, early termination (ET) data will be assigned to what would have been the next scheduled visit where the respective data were scheduled to be collected.
- Data collected on a follow-up visit will be summarized as a separate visit and labeled “Follow-up Visit.”
- Data obtained after the follow-up visit or last dose date plus 30 days (whichever is later) will be excluded from the summaries but will be included in the listings.

3.8.3. Selection of Data in the Event of Multiple Records in an Analysis Visit Window

Depending on the statistical analysis method, single values may be required for each analysis window. For example, change from baseline by visit usually requires a single value, whereas a time-to-event analysis would not require 1 value per analysis window.

If multiple, valid nonmissing measurements exist in an analysis window, records will be chosen based on the following rules if a single value is needed:

- For baseline, the last nonmissing value on or prior to the first dosing date of study drug (GS-5829 or enzalutamide) will be selected, unless specified differently. If there are multiple records with the same time or no time recorded on the same day, the baseline value will be the average of the measurements for continuous data, or the measurement with the lowest severity (eg, normal will be selected over abnormal for safety electrocardiogram [ECG] findings) for categorical data.
- For postbaseline visits:

The record closest to the nominal day for that visit will be selected.

If there are 2 records that are equidistant from the nominal day, the later record will be selected.

If there is more than 1 record on the selected day, the average will be taken for continuous data and the worse severity will be taken for categorical data, unless otherwise specified.

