7.2.1. Summaries of Numeric Laboratory Results

Descriptive statistics will be provided by treatment group for each laboratory test specified in the study protocol as follows:

- Baseline values
- Values at each postbaseline visit
- Change and percentage change from baseline at each postbaseline visit

A baseline laboratory value will be defined as the last measurement obtained on or prior to the date/time of first dose of study drug. Change from baseline to a postbaseline visit will be defined as the visit value minus the baseline value. The mean, median, Q1, Q3, minimum, and maximum values will be displayed to the reported number of digits; StD values will be displayed to the reported number of digits plus 1.

In the case of multiple values in an analysis window, data will be selected for analysis as described in Section 3.8.3. In the event that both central and local lab results are collected in the clinical database, only central lab results will be included in the summary by visits. All central and local laboratory values will be listed.

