7.3. Vital Signs

Descriptive statistics will be provided by treatment group for vital signs as follows:

- Baseline value
- Values at each postbaseline visit
- Change from baseline at each postbaseline visit

A baseline value will be defined as the last available value collected on or prior to the date/time of first dose of study drug. Change from baseline to a postbaseline visit will be defined as the postbaseline value minus the baseline value. Vital signs measured at unscheduled visits will be included for the baseline value selection.

In the case of multiple values in an analysis window, data will be selected for analysis as described in Section 3.8.3.

A by-subject listing of vital signs will be provided by subject ID number and visit in chronological order. High or low values for vital signs will be flagged.

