Electrocardiogram (ECG) analysis results are intended to identify meaningful changes in the QT interval. If potential abnormalities of interest are identified, further analyses may be conducted. Summaries of ECG data will be provided for the Safety Analysis Set for each scheduled time point based on central ECG results. The local ECG assessment results will be used in the data summary if only local ECG measurements are available at a visit/time point. No formal statistical testing is planned.

A by-subject listing for ECG assessment results will be provided by subject ID number and visit in chronological order.

7.5.1. **Corrected QT Intervals**

The QT interval (measured in millisecond [msec]) is a measure of the time between the start of the Q wave and the end of the T wave in the heart's electrical cycle. The QT interval represents electrical depolarization and repolarization of the ventricles. The QT interval is affected by heart rate, and a number of methods have been proposed to correct QT for heart rate.

Corrected QT (QTc) intervals will be derived using Fridericia's correction (QTcF) as follows:

$$QTcF = \frac{QT}{\sqrt[3]{RR}}$$

where QT is measured in msec; RR = 60/Heart Rate (beats per min [bpm]) and RR is measured in seconds

The maximum postdose QTcF interval values obtained during the study will be summarized within the following categories:

- > 450 msec
- > 480 msec
- > 500 msec

The maximum postdose change in QTcF interval values obtained during the study will also be summarized within the following categories:

- > 30 msec
- > 60 msec

QTcF and uncorrected QT values at each visit and time point and change from baseline at each visit and time point will be summarized for the Safety Analysis Set by treatment group using descriptive statistics.

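### The SAP fixes the ECG baseline by dosing date, not dosing time, so in Phase 1b monotherapy the rule as written makes a post-dose tracing the QTcF baseline

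*SAP*

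**What the plan says.** The default baseline rule is in SAP 3.8.3: "For baseline, the last nonmissing value on or prior to the first dosing date of study drug (GS-5829 or enzalutamide) will be selected". It yields only where another section sets a different rule. The same bullet uses safety ECG findings as its example for categorical data, so it plainly covers ECG. It also deals with ties: "If there are multiple records with the same time or no time recorded on the same day, the baseline value will be the average".

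Two safety sections set their own, tighter rule:

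- Laboratory, SAP 7.2.1: "A baseline laboratory value will be defined as the last measurement obtained on or prior to the date/time of first dose of study drug".
- Vital signs, SAP 7.3: "A baseline value will be defined as the last available value collected on or prior to the date/time of first dose of study drug".

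SAP 7.5 defines no ECG baseline, but its outputs need one. SAP 7.5.1 states: "The maximum postdose change in QTcF interval values obtained during the study will also be summarized", with cut-points at 30 and 60 msec, and also tabulates QT and QTcF change by visit and time point. SAP 7.5.2 tabulates change in ventricular rate, PR, RR and QRS.

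On the schedule, Protocol Appendix 2 (ECG footnote) states: "In Phase 1b monotherapy, triplicate ECGs will be collected on C1D1 at pre-dose and 1-4 hrs post-dose". Protocol 8.3 gives the governing definition: "The baseline value will be the last (most recent) pre-treatment value". SAP 7.8 declares no departure from the protocol's safety analyses.

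**The concern.** In monotherapy the Cycle 1 Day 1 visit is the first dosing date, and two sets of ECGs are scheduled on it, one on each side of the dose. A rule that looks only at the date cannot tell them apart, and the last value on that date is the later one.

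Vital signs have the same structure on that day: Appendix 2 takes them before dosing and again at 2 and 4 hours. There the SAP guards against the problem by adding the time. ECG has no such guard.

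A post-dose baseline subtracts any immediate drug effect from every later change. SAP 7.5 says that the purpose of the ECG analysis is to find meaningful QT changes. Safety and tolerability is a Phase 1b primary objective, and SAP section 1 records that the study stopped without entering Phase 2. An error in the direction that conceals prolongation should not be left in the rule.

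**Working it through.** The plan gives no figure for this point, so there is none to reproduce. The check applies each rule to the scheduled ECGs and then works out the effect on the change scores.

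**Step 1. Which ECG becomes baseline?**

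The inputs are the ECG schedules in Protocol Appendices 2 and 3, the definition of study drug as either agent (SAP 3.1.2), and the start of enzalutamide on Study Day 1 in combination (SAP 1.2).

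| Regimen | Date rule (SAP 3.8.3) | Date/time rule (as in SAP 7.2.1 and 7.3) |
|---|---|---|
| Phase 1b monotherapy, clock times recorded | C1D1, 1-4 h post-dose | C1D1 pre-dose |
| Phase 1b monotherapy, no clock times | Average of C1D1 pre- and post-dose | Cannot be applied without a time or a pre-dose label |
| Phase 1b combination | Screening | Screening |

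In combination, neither Protocol 6.5.1 nor the Appendix 3 table schedules an ECG on Study Day 1. The first on-study tracings come at Cycle 1 Day 1, after the enzalutamide lead-in: "triplicate ECGs will be collected on Cycle 1, Day 1 and Day 15 at pre-dose, 1 hour, 2 hours". Screening is therefore selected under either rule.

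**Step 2. Effect on monotherapy change scores.**

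Let B be the pre-dose QTcF, d the acute effect at 1-4 h, and X a later value.

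- Intended change: X − B.
- As written, with clock times: X − (B + d), which is the intended change minus d.
- As written, without clock times and with equal numbers of tracings before and after the dose: X − (B + d/2), which is the intended change minus d/2.
- At the C1D1 post-dose time point the intended change is d. As written with clock times it is about zero, because the record is its own reference.

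If d = 0 there is no systematic shift. If d is negative, later changes are overstated instead.

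**Step 3. Illustration only.**

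Nothing in the documents gives d or the distribution of QTcF change. Assume that the maximum change from a pre-dose baseline is normal with mean μ and SD σ (msec), and that d is the same for every subject. Then P(change > 30) = 1 − Φ((30 − μ + d)/σ).

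For example, with μ = 20 and σ = 12:

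- d = 0: (30 − 20)/12 = 0.83, giving 0.202.
- d = 5: (35 − 20)/12 = 1.25, giving 0.106.
- d = 10: (40 − 20)/12 = 1.67, giving 0.048.

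Over a range of assumptions:

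| μ, σ | Pre-dose baseline | Post-dose, d = 5 | d = 10 | d = 15 |
|---|---|---|---|---|
| 15, 12 | 0.106 | 0.048 | 0.019 | 0.006 |
| 15, 18 | 0.202 | 0.133 | 0.082 | 0.048 |
| 25, 12 | 0.338 | 0.202 | 0.106 | 0.048 |
| 25, 18 | 0.391 | 0.289 | 0.202 | 0.133 |

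Without clock times the loss is smaller: for μ = 25, σ = 18, d = 10 the proportion is 0.289 rather than 0.202. For the >60 msec category with μ = 25 and σ = 18, it falls from 0.026 to 0.006 at d = 10.

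**Step 4. What does not move.**

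The >450, >480 and >500 msec categories, the observed QT and QTcF values, and the by-subject ECG listing do not use a baseline.

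**The case against.** The strongest reply is that nobody would program it this way. Protocol 8.3 asks for a pre-treatment value, SAP 7.8 claims no departure from it, and SAP 7.5.1 speaks of post-dose change. A scheduled post-dose time point that serves as its own baseline makes little sense. All of that is fair evidence of intent, and a careful programmer might well use the pre-dose tracing. It does not cure the text: the stated rule gives a different answer, and the SAP shows in two neighbouring sections that it knows how to say date/time.

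The reply also has force on size. Protocol 1.2.2.2 says that nonclinical work gives no reason to expect QT prolongation, so d may be near zero. The outputs are descriptive, and neither the DLT definition nor the MTD rule uses QTcF change. This limits the consequences and is why the point is not graded higher.

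A reader might go further and infer that the combination baseline is also wrong, or that the two regimens cannot be compared. The documents do not support that. Study drug includes enzalutamide, so the screening ECG is the last scheduled pre-treatment value, as Protocol 8.3 requires, and the Cycle 1 Day 1 pre-dose tracing is correctly post-baseline. No between-regimen comparison is planned, and SAP 3.5 and 7.5 rule out formal testing. What remains is attribution: the screening ECG can precede the first GS-5829 dose by about 11 days (14 − 3) to 45 days (28 + 14 + 3), so change from it combines the enzalutamide lead-in with GS-5829. That is a limitation of the display, not an error.

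A reader might also infer that a single tracing will replace the triplicate mean. That would follow only if the three tracings are stored with different clock times, and the documents do not say how they are stored.

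**Conclusion.** The point holds for Phase 1b monotherapy and should be fixed. As written, SAP 3.8.3, with no override in SAP 7.5, takes the Cycle 1 Day 1 post-dose ECG as baseline, or a pre/post average if clock times are absent. Either result contradicts Protocol 8.3.

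The consequence is a Day 1 post-dose change of about zero (with clock times) and later changes understated by d, or by d/2 in the averaged case. This reaches the >30 and >60 msec categories and the QT and QTcF change tables. The PR, RR, QRS and ventricular-rate change summaries rest on the same wrong baseline. The size is unknown and is nil if there is no acute effect; the probabilities above show direction under assumed values and are not estimates for this trial. The conclusion assumes that the rule is applied literally and that both Day 1 ECG sets were obtained.

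To say that the plan hides QT prolongation would be too strong: the absolute QTcF categories and the listings would still show long intervals.

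**What to change.** Add one sentence to SAP 7.5, matching the approach of 7.2.1 and 7.3: the ECG baseline is the mean of the last triplicate ECG recorded before the date/time of the first dose of study drug. Add that a record without a clock time is classed by its nominal pre-dose or post-dose label. The sentence also settles the triplicate question, whatever the storage format, and leaves the combination baseline at the last pre-enzalutamide ECG, normally screening.

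Optionally, for the combination cohorts, add a supplementary table of QTcF change from the Cycle 1 Day 1 pre-dose triplicate, leaving that triplicate out of the post-dose maximum in that table. It would help to separate GS-5829 from the enzalutamide lead-in.

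The cost is one or two sentences and a small change to the baseline derivation, plus one table if the option is taken. The tracings are already scheduled, so no new data are needed. If the SAP is already final, the clarification belongs in the clinical study report, as SAP section 1 provides.

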4. SUBJECT DISPOSITION

4.1. Subject Enrollment and Disposition

A summary of subject enrollment will be provided by treatment group for each investigator and overall. The summary will present the number and percentage of subjects enrolled. For each column, the denominator for the percentage calculation will be the total number of subjects analyzed for that column.

A summary of subject disposition will be provided by treatment group. This summary will present the number of subjects screened, the number of subjects enrolled, and the number of subjects in each of the categories listed below:

- Full Analysis Set
- Safety Analysis Set
- Discontinued GS-5829 with reasons for discontinuation
- Discontinued Enzalutamide with reasons for discontinuation
- Discontinued the study with reasons for discontinuation of study

For the status of study drug (GS-5829 and Enzalutamide) and study completion and reasons for premature discontinuation, the number and percentage of subjects in each category will be provided. The denominator for the percentage calculation will be the total number of subjects in the Full Analysis Set corresponding to that column.

The following by-subject listings will be provided by subject identification (ID) number in ascending order to support the above summary tables:

- Reasons for premature study drug or study discontinuation

4.2. Extent of Study Drug Exposure and Adherence

Extent of exposure to GS-5829 will be examined by assessing the total duration of exposure to GS-5829 and the level of adherence to the GS-5829 specified in the protocol.

4.2.1. Duration of Exposure to GS-5829

Total duration of exposure to GS-5829 will be defined as last dosing date of GS-5829 minus first dosing date plus 1, regardless of any temporary interruptions in GS-5829 administration and will be expressed in weeks using up to 1 decimal place (eg, 4.5 weeks).

If the last GS-5829 dosing date is missing, the latest date among the GS-5829 end date, clinical visit date, laboratory sample collection date, and vital signs assessment date that occurred during the on-treatment period will be used.

Partial dose start or stop dates for each dosing period will be imputed using the following algorithm:

- For dose stop date: If day and month are missing but year is available, then the imputed day and month will be the earliest from the following dates: 31 DEC, death date, end of GS-5829 treatment (EOT) date, and (start date of the next dosing period -1); If day is missing but the month and year are available, then the imputed day will be the earliest from the following dates: last day of the month, death date, EOT date, and (start date of the next dosing period - 1).
- For dose start date: If day and month are missing but year is available, then the imputed day and month will be the earliest from the following dates: later of (01 JAN, and (stop date of the previous dosing period + 1)), and stop date of the associated dosing period; If day is missing but the month and year are available, then the imputed day will be the earliest from the following dates: later of (first day of the month, and (stop date of the previous dosing period + 1)), and stop date of the associated dosing period.

The total duration of exposure to GS-5829 will be summarized using descriptive statistics and percentage of subjects exposed through the following time periods: 1 day, 4 weeks, 8 weeks, 16 weeks, 24 weeks, 36 weeks, 48 weeks and 60 weeks. Summaries will be provided by treatment group for the Safety Analysis Set.

